## GI Dysbiosis Participants

Following informed consent and pre-transplant, enrolled participants will have their blood collected for Hepatitis BsAg, Hepatitis C Ab, HIV, Syphilis serologies unless these serologies were performed within 3 months of enrollment. Blood is collected for these pathogens to determine their serostatus at the time of study enrollment and prior to receiving FMT.

All participants will be assessed at day 1 by the physician-investigator. A medical history and physical examination will be performed. In addition, optional blood and stool samples may be collected from IBD/IBS participants who consented for these samples prior to the FMT and at weeks 4, 12 and 6 months from FMT.

The participants will receive lyophilized FMT (LYO-FMT) or frozen FMT enemas using stool collected from healthy, screened donor(s). Participants will receive FMT treatment via retention enema(s) twice weekly for 4 weeks. If there is symptom improvement after 4 weeks of treatment, then the participants will receive FMT treatment once weekly for 4 additional weeks. If the participant does not experience symptom improvement after the initial 4 weeks of treatment, the physician-investigator will discuss options with the participant and a mutual decision will be reached to pursue an additional 4 weeks of FMT treatment or withdraw from the study and pursue usual care. When continued improvement is seen then the participants will receive FMT maintenance; the frequency of FMT treatment is participant dependent and is at the discretion of the physician-investigator and is based upon clinical exam and symptomatic improvement. If no improvement is seen after the 8th FMT, then the participant will be withdrawn from the study and s/he reverts to usual care for his/her condition. Participants can opt to receive maintenance FMT in the clinic or be trained by study staff for home administration.

At the time of each study visit and follow up, participants will be assessed for clinical response, including bowel movements and adverse reactions. Any participant who reports worsening symptoms or AE/SAE will return to the clinic for assessment by the physician investigator. At that time, the participant will undergo a physical exam. Additional tests may be ordered (i.e. blood work) at the discretion of the treating physician investigator.

From the previous UC FMT trial, it was discovered that the participants who responded to the initial series of FMT, required ongoing maintenance FMT to remain UC symptom-free. Following the completion of 6-month FMTs, participants will have the option of continuing with the maintenance FMT which can range from one FMT every 2 weeks to every 6 months depends on the individual. In the event that it is not possible for the participant to return to the clinic or requires significant time/travel commitments to receive the FMTs, either the participant or a household member will be trained to store and to administer the lyophilized FMT at home, if the participant is willing to do so.

The home maintenance FMT will be offered only when all the following conditions are met:

1. There is clinical evidence of improvement following the initial FMT series.
2. Participant agrees to continue with maintenance FMT
3. Participant or a household can safely administer FMT at home as assessed by the research staff.
4. There is availability of lyophilized FMT for distribution

5. The participant or delegate is willing to notify the research staff of the progress and request for lyophilized FMT to be available either by picking them up or be shipped 3 weeks prior to needing additional lyophilized FMT.
6. Participant agrees to pay for the shipping supplies and the shipment of FMTS

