### **Secondary Outcome Measurements for participants with IBD, MC or IBS:**

1. Evaluate efficacy and safety of FMT in patients with chronic gastronintestinal dysbiosis and antimicrobial resistant organism in the gut

2. Evaluate the Ulcerative Colitis Disease Activity Index from baseline and following each FMT using partial-MAYO score.
3. Evaluate Crohn's Diseases Activity Index (CDAI) change from baseline 4 weeks, 12 weeks and 1 year post-FMT.
4. Evaluate Microscopic colitis response to FMT using physician's global assessment and number of unformed bowel movements per 24 hours
5. Evaluate Irritable Bowel Syndrome Severity Scoring System (IBS-SSS) grade assessment change from baseline, 4 weeks, 12 weeks and 1 year post-FMT.

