### **FMT Side Effects**

Possible FMT Side Effects	Frequency that the side effect has been reported
Hard stool	10%
Increase in flatulence or passing gas	10%
Stomach discomfort	8%
Increase appetite	3%
Nausea	2%
Minor temporary pressure or discomfort in the rectum	1%

There has been a report of transmission of multi-drug resistant organism (MDRO) to patients who received FMT from a donor, whose stool was not screened for the MDRO.

There may be a small risk of transmission and infection due to MDRO. However, the donor's stool samples used at Vancouver Island Health Authority routinely undergo screening for MDRO. The donor's blood and stool are regularly tested for transmissible infectious organisms that may cause disease. If a donor and/or their stool sample shows abnormal result(s), such stool samples will not be considered for FMT processing.

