### **Enrollment stopping rules**

If the DMC decided that there were a pattern consistent with an important increase in frequency of the occurrence of one or more types of SAEs then a review by the DMC Chair will be requested.

The DMC, upon review of the participant-specific reported SAEs, will: Convene a meeting of the full DMC for the purpose of providing a recommendation to the investigator regarding cessation or continuation of enrollment in the study. Such recommendation will be formally provided within 24 hours of such meeting and will not be influenced by actions or opinion of the any of the investigators; Recommend that enrollment in the study be halted if as many as three (3) participants that received treatment with FMT were reported to experience the same or substantially similar types of SAE and the DMC concluded that such SAEs could be reasonably related to treatment with FMT; Recommend that enrollment in the study be halted if any one participant who received treatment with FMT were reported to experience an SAE that had fatal or life-threatening outcome and the DMC concluded that such SAE could be reasonably related to FMT.

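### Dysbiosis participants who do not improve leave the study itself, and no AE/SAE collection is scheduled after that, so the safety outcome and both halting rules can under-count

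*Combined protocol and SAP*

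**What the plan says.** Under *GI Dysbiosis Participants*, the initial schedule is: "Participants will receive FMT treatment via retention enema(s) twice weekly for 4 weeks". For a participant without symptom improvement at that point, "a mutual decision will be reached to pursue an additional 4 weeks of FMT treatment or withdraw from the study". A later sentence in the same paragraph adds: "If no improvement is seen after the 8th FMT, then the participant will be withdrawn from the study and s/he reverts to usual care".

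Safety observation in this group is described in two sentences of that section. The first is: "At the time of each study visit and follow up, participants will be assessed for clinical response, including bowel movements and adverse reactions". The second is: "Any participant who reports worsening symptoms or AE/SAE will return to the clinic for assessment by the physician investigator". *Adverse Event Reporting* adds that participants are advised to report effects, and that events are recorded and passed on once the investigator knows of them.

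*Primary Outcome Measurements* sets symptom-score assessments at 4 weeks, 12 weeks and 1 year. It neither exempts withdrawn participants nor says that they are still followed.

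Three other parts of the plan depend on these data:

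- The first secondary outcome: "Evaluate efficacy and safety of FMT in patients with chronic gastronintestinal dysbiosis".
- The first halting rule in *Enrollment stopping rules*, whose trigger is: "as many as three (3) participants that received treatment with FMT were reported to experience the same or substantially similar types of SAE". The committee must also find those events reasonably related to FMT.
- The second halting rule there, met by one related SAE with a fatal or life-threatening outcome.

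Both rules work on reported events. According to the section on trial steering and the DMC, the investigator supplies those reports.

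**The concern.** Ending treatment and ending observation are different decisions, and the plan joins them. Once a non-improver has left the study, there is no study visit at which an adverse reaction would be asked about. An SAE managed in usual care enters the trial record only if the participant or a treating clinician reports it.

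The loss is selective, because withdrawal depends on failure to improve. Later safety data would come mostly from participants who benefited, and participants whose condition did not respond, or who were harmed, would be under-represented. The halting rules are worded to cover everyone who received FMT, but they would be applied to a count that is solicited from only part of that group.

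**Working it through.** **Step 1: timing.** 2 FMTs per week × 4 weeks = 8 FMTs, so the 8th FMT falls at about the end of week 4. The mutual-decision sentence applies at the same moment. One sentence allows a non-improver to continue and the other requires withdrawal; the documents do not reconcile them. Under either route a withdrawn participant has left before the 12-week and 1-year time points.

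**Step 2: what remains after withdrawal.**

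| Source of safety information | Scheduled after withdrawal? |
|---|---|
| Assessment at study visits and follow-up | Not stated; the participant is no longer in the study |
| 12-week and 1-year assessments | Not stated; defined for symptom scores |
| Return to clinic on reporting an event | Only if the participant reports |
| SAE reports to the DMC | Only events the investigator knows of |

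**Step 3: illustration for the three-participant rule.** The plan has no figure of its own on this point to reproduce. Inputs:

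- n = 50 dysbiosis participants (*Proposed sample size*).
- p = true risk per participant of one type of related SAE. Assumed 10%; the documents give none.
- w = share withdrawn. Assumed 30% to 76%. The upper value is 1 − 0.24, using the 24% FMT-arm response that the sample-size section takes from a UC trial.
- d = share of withdrawn participants' SAEs that arise after withdrawal and go unreported. Assumed 0.5.

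The reported risk is p′ = p(1 − w·d), and the chance of reaching three is 1 − P(X ≤ 2) with X ~ Binomial(50, p′). Events are taken as independent, with the same risk in improvers and non-improvers.

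- Complete follow-up: p′ = 0.100; 1 − (0.0052 + 0.0286 + 0.0779) = 0.888.
- w = 0.30: p′ = 0.10 × (1 − 0.15) = 0.085; 1 − (0.0118 + 0.0547 + 0.1245) = 0.809.
- w = 0.50: p′ = 0.10 × (1 − 0.25) = 0.075; result 0.734.
- w = 0.76: p′ = 0.10 × (1 − 0.38) = 0.062; 1 − (0.0408 + 0.1347 + 0.2181) = 0.606.

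At p = 5% the chance is 0.459 with complete follow-up, 0.358 at w = 0.30 and 0.202 at w = 0.76.

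**Step 4: the one-event rule.** The chance of at least one reported event is 1 − (1 − p′)^50. At an assumed 2% risk with d = 0.5:

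- Complete follow-up: 1 − 0.98^50 = 0.636.
- w = 0.30: p′ = 0.017; 1 − 0.983^50 = 0.576.
- w = 0.76: p′ = 0.0124; 1 − 0.9876^50 = 0.464.

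**Step 5: adding the ARO group.** The halting rules are not limited to dysbiosis participants. Suppose the 20 ARO participants carry the same 10% risk and all their events are captured. With complete follow-up of all 70, the chance of reaching three is 0.976. For n = 20 and p = 0.10, the probabilities of 0, 1 and 2 events are 0.1216, 0.2702 and 0.2852, so the cumulative values are 0.1216, 0.3917 and 0.6769. Combining these with Step 3:

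- w = 0.30: 1 − (0.0118 × 0.6769 + 0.0547 × 0.3917 + 0.1245 × 0.1216) = 0.955.
- w = 0.76: 1 − (0.0408 × 0.6769 + 0.1347 × 0.3917 + 0.2181 × 0.1216) = 0.893.

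The direction is unchanged and the loss is smaller.

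**The case against.** The strongest reply is that observation does not stop dead. Someone has to judge that there is no improvement after the 8th FMT, which implies an assessment at about that time, and assessments include adverse reactions. Participants are told to report effects, and any who do are brought back. The 12-week and 1-year assessments do not exclude non-improvers. The consent text is not among the documents reviewed and may cover reporting after withdrawal. All of this stands. It means that events can be missed, not that they will be, and that withdrawn participants can still add to the count. It does not supply a scheduled contact after withdrawal.

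A reader might go further in three ways that the documents do not support.

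- *That the plan itself names a delayed harm.* The side-effects section says only: "There may be a small risk of transmission and infection due to MDRO". It gives no timing, and it adds that donor stool is routinely screened.
- *That the 3 months in the ARO group is a safety window to copy.* It is a stool-culture schedule for testing eradication.
- *That most of the safety information is lost.* If all 50 × 0.76 = 38 non-responders left at week 4, 38 × 48 = 1,824 of 50 × 52 = 2,600 participant-weeks (70%) would be unobserved. With only the other 12 observed, the chance of reaching three at a 10% risk would be 0.11. This is a worst case. It applies a UC-trial response rate to a symptom-improvement criterion across several conditions, assumes that nobody reports after leaving, omits the ARO group, and counts a full year.

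The rules also halt enrollment only, so events after recruitment closes cannot trigger them.

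**Conclusion.** The gap is real, and it is one of wording and design rather than arithmetic. The plan withdraws non-improving dysbiosis participants from the study and schedules no AE/SAE collection for them afterwards. It also leaves open whether the 12-week and 1-year assessments still apply. The safety outcome and both halting rules can therefore under-count, selectively, among participants who did not improve.

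The size cannot be determined from the documents, which give no SAE rate, withdrawal share or share of late events. Under the stated assumptions (10% risk, 50 dysbiosis participants, d = 0.5), the chance of reaching three falls from 0.89 to between 0.81 and 0.61. It falls less if fully observed ARO participants share the same risk. The change is worth making because it costs little and the missing data are not missing at random.

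**What to change.** 1. Under *GI Dysbiosis Participants*, separate stopping FMT from leaving the study. Everyone who received at least one FMT stays in AE/SAE collection, unless consent is withdrawn, through a stated period that uses a time point already planned for this group, for example the 12-week assessment. State whether it is counted from the first or the last FMT. For someone stopping at week 4, counting from the first leaves 12 − 4 = 8 weeks of observation, and counting from the last leaves 12. The existing coordinator can make the contact by phone or REDCap.
2. In the DMC section and *Enrollment stopping rules*, state that SAEs found this way go to the DMC and count toward both halting rules.
3. Reconcile *Primary Outcome Measurements* with *GI Dysbiosis Participants* on follow-up after withdrawal.
4. Reconcile the two sentences on what happens after the initial 4 weeks and after the 8th FMT. This point takes no position on which should govern and changes no treatment rule.

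The cost is a protocol and consent wording change and modest coordinator time, for at most about 38 participants if the 76% assumption held.

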### **Primary Outcome Measurements:**

For the participants with chronic GI dysbiosis, the efficacy of FMT treatment will be based on improvement in participant's symptom score from baseline (pre-transplant) to intervention (post-transplant) 4 weeks, 12 weeks and 1 year following FMT. For participants with ARO colonization, determination of clearance of ARO based on stool culture for ARO at baseline, day 7, day 30 and 3 months following last FMT.

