### **Crohn's Disease**

CDAI is a validated instrument used in adults with active Crohn's disease. The index consists of eight factors, 2 of which are subjective: stool habits; pain; general well being; features of extra intestinal disease; use of opiates for diarrhea; abdominal mass; hematocrit (hct); and percentage of body weight below standard. Scores range from 0 to ~ 600: > 450 is severe disease; 220 – 450 moderately active disease; 150 – 219 mildly active disease. Clinical remission is defined as a CDAI score <150, clinical response is either a CDAI score <150 or a CDAI reduction of ≥100 from baseline.

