### **The proposed type of statistical analyses**

The clinical response rate will be determined using standard binary outcome protocols. Also, logistic regression and survival analysis methods will be performed. The primary endpoints of clinical response, and treatment failure will be analyzed by logistical regression.

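### Non-improvers leave the study at about week 4, so the week-12 and 1-year primary scores come mainly from early improvers, and the response-rate denominator is not stated

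*Combined protocol and SAP*

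**What the plan says.** Under Primary Outcome Measurements, efficacy in the chronic GI dysbiosis group rests on improvement in symptom score "from baseline (pre-transplant) to intervention (post-transplant) 4 weeks, 12 weeks and 1 year following FMT". The secondary outcomes for Crohn's disease and IBS, and the Ulcerative Colitis section, use the same three times.

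The section GI Dysbiosis Participants sets the schedule: "Participants will receive FMT treatment via retention enema(s) twice weekly for 4 weeks". For a participant who has not improved by then, "a mutual decision will be reached to pursue an additional 4 weeks of FMT treatment or withdraw from the study and pursue usual care". Later in the same paragraph: "If no improvement is seen after the 8th FMT, then the participant will be withdrawn from the study". Maintenance is for the others: "When continued improvement is seen then the participants will receive FMT maintenance".

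The section on the proposed type of statistical analyses is three sentences long. It names binary-outcome methods, logistic regression and survival analysis, and says: "The primary endpoints of clinical response, and treatment failure will be analyzed by logistical regression". It defines neither clinical response nor treatment failure, and it gives no analysis population and no rule for missing scores or withdrawals. No section provides for collecting scores after a participant has been withdrawn.

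**The concern.** Both sentences about non-improvers take the person out of the study, not only off FMT. Whether someone is still there to be scored at week 12 and 1 year therefore depends on an early value of the outcome itself. Early improvers who later relapse do stay in, so the selection is on early improvement, not on final success. Its direction is known: it favours FMT. The design section describes an open-label trial with no control arm, so nothing in the data would expose the effect.

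Two results are at stake. Mean score change at two of the three primary time points would describe a selected subgroup. The response rate at those time points would depend on a denominator that the plan leaves open. Scores that were never collected cannot be recovered at the analysis stage.

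The timing is also inconsistent. At the end of week 4 one sentence allows a non-improver to continue for 4 more weeks, while another withdraws a non-improver after the 8th FMT, which is the same point. Nothing says when a non-improver who takes the extra 4 weeks is withdrawn.

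**Working it through.** **Inputs from the plan.** Dysbiosis sample size 50; assumed FMT response 24% and placebo response 5%, alpha 5%, power 80% (section on sample size); FMT twice weekly for 4 weeks.

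**Inputs that are assumptions.** Fraction retained, r: 80%, 60% or 40%. Correlation between week-4 and week-12 score change: 0.3, 0.5 or 0.7. The documents give neither.

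**The plan's own figure.** The two-proportion formula with unpooled variance and two-sided alpha gives (1.960 + 0.842)² × (0.05 × 0.95 + 0.24 × 0.76) / 0.19² = 7.849 × 0.2299 / 0.0361 ≈ 50. This matches the stated 50, but as a per-arm number for a two-arm trial. The present point does not depend on it; only N = 50 and the 24% are used below.

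**Timing.** 2 per week × 4 weeks = 8 FMTs, so the 8th falls at the end of week 4. If the extra 4 weeks are taken, withdrawal comes at about week 8. Both precede week 12.

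**Response rate.** A true 24% is 12 of 50. Suppose all 12 responders are among those retained and only observed participants are analysed. The apparent rate is 12 / (50r), an inflation of 1/r.

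| Retained | Observed-only rate | Inflation | Withdrawn counted as failures |
|---|---|---|---|
| 80% | 12/40 = 30% | 1.25 | 12/50 = 24% |
| 60% | 12/30 = 40% | 1.67 | 24% |
| 40% | 12/20 = 60% | 2.5 | 24% |

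The same calculation by share of the 38 non-responders withdrawn gives 12/40.5 = 29.6% (a quarter withdrawn), 12/31 = 38.7% (half), 12/21.5 = 55.8% (three quarters) and 12/12 = 100% (all).

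**Mean score change.** Let week-4 and week-12 changes be bivariate normal in SD units with true mean zero, and keep the best fraction r on week-4 change. The mean week-4 change among those kept is φ(z)/r, where z is the cut-off that retains r. This is 0.350, 0.644 and 0.966 SD for r = 0.8, 0.6 and 0.4. Multiplying the unrounded values by the correlation gives the apparent week-12 improvement:

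| Retained | Correlation 0.3 | 0.5 | 0.7 |
|---|---|---|---|
| 80% | 0.10 SD | 0.17 SD | 0.24 SD |
| 60% | 0.19 SD | 0.32 SD | 0.45 SD |
| 40% | 0.29 SD | 0.48 SD | 0.68 SD |

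A simulation under a different selection rule (keep anyone with a week-4 change above zero, which retains half) gives 0.24, 0.40 and 0.56 SD for the three correlations. If the true mean change is 0.5 SD at both times, that rule retains 69% and the later mean reads 0.65 to 0.86 SD, an excess of about 0.15 to 0.36 SD.

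**The case against.** The strongest reply is that the plan never commits to averaging observed scores. The analysis section treats the primary endpoints as binary, and a participant withdrawn for lack of improvement has a known status: non-response. Treatment failure is a natural place to put such people, and in a survival analysis their withdrawal could be the event. On that reading, what remains is an undefined term that wording can repair. The magnitudes also rest on assumed retention and correlation, on strict selection at week 4 although some non-improvers may continue, and on a 24% taken from an ulcerative colitis trial and applied to a mixed group. Finally, the anchor of the 4-week assessment (first or last FMT) is not stated, and scores taken after stopping FMT would reflect usual care.

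Part of this stands. The response rate is unaffected if withdrawals count as failures, and the sizes are illustrations, not estimates. But the plan does not say that withdrawals are failures, nor whether they are events or censored in the survival analysis. A failure rule also does nothing for score change, which is how the primary outcome section expresses efficacy; with no later scores from those withdrawn, an all-participant score analysis would have to rest on imputation. Continuation past week 4 weakens the selection but still ends in an unspecified withdrawal. If the 4-week assessment is counted from the last FMT, even that time point falls after withdrawal, which makes matters worse. Stopping ineffective treatment is reasonable; it does not require ending follow-up.

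**Conclusion.** The concern holds and should be treated as a required change. By the plan's own rule, week-12 and 1-year scores will be available mainly for early improvers, and the mean change observed at those times is biased toward benefit. Counting the 4-week assessment from the start of FMT, the week-4 outcome is largely unaffected.

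The size cannot be read from the documents. With 80% to 40% retained, an observed-only response rate is inflated 1.25- to 2.5-fold (24% reads as 30% to 60%), on the further assumption that every responder is retained. With no true mean change, the apparent week-12 improvement is 0.10 to 0.68 SD, with 0.32 SD at 60% retained and correlation 0.5. The response-rate part is conditional: it disappears if withdrawn participants are counted as failures. Spontaneous improvement is a separate limitation of the uncontrolled design, which the fix does not address.

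**What to change.** 1. **Analysis section.** Analyse response at every time point among all participants who received at least one FMT. Define treatment failure to include withdrawal for lack of improvement, and count a missing score as non-response. Because that last rule also turns unrelated missed visits into failures, add a sensitivity analysis that handles those separately. State whether withdrawal is an event in the survival analysis. Label any week-12 or 1-year mean score change in retained participants as conditional on early improvement.
2. **GI Dysbiosis Participants.** Separate stopping FMT from leaving the study. From those who stop, collect patient-reported items at week 12 and 1 year by phone or questionnaire: IBS-SSS, the stool-frequency and bleeding items of the partial Mayo score, the number of unformed stools, and the CDAI symptom items. Use them for an all-treated score-change analysis and for safety, not to overturn the non-response rule in item 1.
3. **Timing.** Reconcile the week-4 option to continue with the 8th-FMT rule, and state one withdrawal time for those who take the extra 4 weeks.

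Items 1 and 3 cost wording, plus the one added analysis. Item 2 costs 50 × (1 − r) × 2 contacts: 20, 40 or 60 for 80%, 60% or 40% retained. Some scores will be partial, since the CDAI components "abdominal mass; hematocrit (hct); and percentage of body weight below standard" and the physician's global assessments may not be obtainable remotely. Scores after stopping will reflect usual care. The reported week-12 and 1-year response rates will be lower than observed-only rates.
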